4.2.3 Rationale for Endpoints

4.2.3.1 Efficacy Endpoints

Although drug efficacy is not a primary objective of the study, effects on the tumor will be evaluated for both descriptive presentation and to aid in informing study size for future phase trials with an efficacy endpoint. The main mechanism for doing so will be via histopathologic review of the radical cystectomy specimen. Historically patients with MIBC who undergo 'window of opportunity' chemotherapy are defined as responders if they achieve a pT1 stage or less. For the purposes of this study a similar efficacy endpoint will be utilized for MIBC patients. In the case of NMIBC a pT0 status will be used to identify complete response.

4.2.3.2 Biomarker Research

The identification of specific signatures of tissue response and the association with anti-tumor immune activation will serve a secondary objective to the proposed study. Whenever possible normal tissue from the same patient will be utilized as a control to comparative analysis with tumor specimens after treatment. Analyses will include, but not be limited to, studying signals of anti-cancer immunological activity by evaluating the frequency of CD4 and CD8 T cells in tumor tissues (pre- and post-therapy or untreated and treated cohorts). We will also evaluate tissue for signals of biomarker activity by evaluating surgical specimens for established and not-so-established markers of response to pembrolizumab (e.g. TILS, PD-1 and PD-L1 levels) compared to pre-treatment biopsy samples. In addition, pre- and post-treatment tumors will be assigned to intrinsic basal and luminal subtypes by whole genome mRNA expression profiling (with the assistance of collaborator [name]). Additionally, we will collaborate with Merck Research Laboratories (MRL) in looking at PDL1/PD1 and their panel of gene expression signatures of T-cell activity, APC activity, etc. using, for example, the nanostring platform.

5.1 METHODOLOGY

5.2 Entry Criteria

5.1.1 Diagnosis/Condition for Entry into the Trial

- **Scenario 1: Muscle invasive bladder cancer (MIBC):** Histologically confirmed, by MD Anderson pathologic review, diagnosis of muscle invasive bladder cancer (cT2 or greater). No planned systemic chemotherapy prior to radical cystectomy by standard practice risk stratification, patient refusal, and/or patient ineligibility.

- **Scenario 2: Non-muscle invasive bladder cancer (NMIBC):** Histologically confirmed, by MD Anderson pathologic review, diagnosis of non-muscle invasive bladder cancer (cT1 or less). No planned systemic chemotherapy prior to radical cystectomy by standard practice risk stratification, patient refusal, and/or patient ineligibility. Prior intravesical therapies, whether BCG, chemotherapy or otherwise, will remain eligible.

5.1.2 Subject Inclusion Criteria

In order to be eligible for participation in this trial, the subject must:

1. Be willing and able to provide written informed consent
2. Be ≥ 18 years of age
3. Have absence of metastatic disease as determined by conventional imaging studies and be considered a good surgical candidate by the treating physician.
4. Be willing to participate in the collection of blood and tissue for banking and future correlative studies as specified in the Study Flow Chart (Section 6.0).
5. Have a performance status of 0 or 1 on the ECOG Performance Scale.
6. Demonstrate adequate organ function as defined in Table 1, all screening labs should be performed within 14 days of treatment initiation.

Table 1 Adequate Organ Function Laboratory Values:

System	Laboratory Value
Hematological	
Absolute neutrophil count (ANC)	$\geq 1,500 / \text{mcL}$
Platelets	$\geq 100,000 / \text{mcL}$
Hemoglobin	$\geq 9 \text{ g/dL}$ or $\geq 5.6 \text{ mmol/L}$ without transfusion or EPO dependency within 7 days of assessment
Renal	
Serum creatinine OR	$\leq 1.5 \times \text{upper limit of normal (ULN)}$ OR

Measured or calculated creatinine clearance ^a (GFR can also be used in place of creatinine or CrCl)	≥ 30 mL/min for subject with creatinine levels > 1.5 X institutional ULN
Hepatic	
Serum total bilirubin	≤ 1.5 X ULN OR
	Direct bilirubin ≤ ULN for subjects with total bilirubin levels > 1.5 ULN
AST (SGOT) and ALT (SGPT)	≤ 2.5 X ULN OR ≤ 5 X ULN for subjects with liver metastases
Albumin	≥ 2.5 mg/dL
Coagulation	
International Normalized Ratio (INR) or Prothrombin Time (PT)	≤ 1.5 X ULN unless subject is receiving anticoagulant therapy as long as PT or PTT is within therapeutic range of intended use of anticoagulants
Activated Partial Thromboplastin Time (aPTT)	≤ 1.5 X ULN unless subject is receiving anticoagulant therapy as long as PT or PTT is within therapeutic range of intended use of anticoagulants
^a Creatinine clearance should be calculated per institutional standard.	

7. Female subject of childbearing potential should have a negative urine or serum pregnancy within 72 hours prior to receiving the first dose of study medication. If the urine test is positive or cannot be confirmed as negative, a serum pregnancy test will be required.
8. Female subjects of childbearing potential (Section 5.7.2) must be willing to use an adequate method of contraception as outlined in Section 5.7.2 – Contraception, for the course of the study through 120 days after the last dose of study medication.

Note: Abstinence is acceptable if this is the usual lifestyle and preferred contraception for the subject.

9. Male subjects of childbearing potential (Section 5.7.2) must agree to use an adequate method of contraception as outlined in Section 5.7.2- Contraception, starting with the first dose of study therapy through 120 days after the last dose of study therapy.

Note: Abstinence is acceptable if this is the usual lifestyle and preferred contraception for the subject.

5.1.3 Subject Exclusion Criteria

The subject must be excluded from participating in the trial if the subject:

1. Is currently participating and receiving pembrolizumab or has participated in a study of an investigational agent and received pembrolizumab or used an investigational device within 4 weeks of the first dose of study treatment.
2. Has a diagnosis of immunodeficiency or is receiving systemic steroid therapy or any other form of immunosuppressive therapy within 7 days prior to the first dose of study treatment.
3. Has a known history of active TB (Bacillus Tuberculosis).
4. Has a known history of hypersensitivity to pembrolizumab or any of its excipients.
5. Has had prior systemic anti-cancer therapy for the treatment of bladder cancer. Prior intravesical therapies, whether BCG [including but not limited to: Persistent high-grade disease or recurrence within 6 months of receiving at least two courses of intravesical BCG (at least five of six induction doses and at least two of three maintenance doses); or T1 high-grade disease at the first evaluation following induction BCG alone (at least five of six induction doses)], chemotherapy or otherwise, will remain eligible.
6. Has any other malignancy diagnosed within 2 years of screening with the exception of basal or squamous cell skin cancer, or non-invasive cancer of the cervix, or any other cancer deemed by the treating physician to be of low-risk for progression or patient morbidity during the study period.
7. Has known metastatic disease as determined by conventional staging studies
8. Has active autoimmune disease that has required systemic treatment in the past 2 years (i.e. with use of disease modifying agents, corticosteroids or immunosuppressive drugs). Replacement therapy (e.g., thyroxine, insulin, or

physiologic corticosteroid replacement therapy for adrenal or pituitary insufficiency, etc.) is not considered a form of systemic treatment.

9. Has known history of, or any evidence of active, non-infectious pneumonitis.
10. Has a clinically significant active infection requiring systemic therapy.
11. Has a history or current evidence of any condition, therapy, or laboratory abnormality that might confound the results of the trial, interfere with the subject's participation for the full duration of the trial, or is not in the best interest of the subject to participate, in the opinion of the treating physician.
12. Is pregnant or breastfeeding, or expecting to conceive or father children within the projected duration of the trial, starting with the pre-screening or screening visit through 120 days after the last dose of trial treatment.
13. Has received prior therapy with an anti-PD-1, anti-PD-L1, or anti-PD-L2 agent.
14. Has a known history of Human Immunodeficiency Virus (HIV) (HIV 1/2 antibodies).
15. Has known active Hepatitis B (e.g., HBsAg reactive) or Hepatitis C (e.g., HCV RNA [qualitative] is detected).
16. Has received a live vaccine within 30 days of initiation of study therapy. Note: Seasonal influenza vaccines for injection are generally inactivated flu vaccines and are allowed; however intranasal influenza vaccines (e.g., Flu-Mist®) are live attenuated vaccines, and are not allowed.

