phosphatases SHP-1 and SHP-2 to the ITSM motif within its cytoplasmic tail, leading to the dephosphorylation of effector molecules such as CD3 ζ , PKC θ and ZAP70 which are involved in the CD3 T-cell signaling cascade. The mechanism by which PD-1 down modulates T-cell responses is similar to, but distinct from that of CTLA-4 as both molecules regulate an overlapping set of signaling proteins. PD-1 was shown to be expressed on activated lymphocytes including peripheral CD4+ and CD8+ T-cells, B-cells, Tregs and Natural Killer cells. Expression has also been shown during thymic development on CD4-CD8- (double negative) T-cells as well as subsets of macrophages and dendritic cells. The ligands for PD-1 (PD-L1 and PD-L2) are constitutively expressed or can be induced in a variety of cell types, including non-hematopoietic tissues as well as in various tumors. Both ligands are type I transmembrane receptors containing both IgV- and IgC-like domains in the extracellular region and contain short cytoplasmic regions with no known signaling motifs. Binding of either PD-1 ligand to PD-1 inhibits T-cell activation triggered through the T-cell receptor. PD-L1 is expressed at low levels on various non-hematopoietic tissues, most notably on vascular endothelium, whereas PD-L2 protein is only detectably expressed on antigen-presenting cells found in lymphoid tissue or chronic inflammatory environments. PD-L2 is thought to control immune T-cell activation in lymphoid organs, whereas PD-L1 serves to dampen unwarranted T-cell function in peripheral tissues. Although healthy organs express little (if any) PD-L1, a variety of cancers were demonstrated to express abundant levels of this T-cell inhibitor. PD-1 has been suggested to regulate tumor-specific T-cell expansion in subjects with melanoma (MEL). This suggests that the PD-1/PD-L1 pathway plays a critical role in tumor immune evasion and should be considered as an attractive target for therapeutic intervention.

Pembrolizumab is a potent and highly selective humanized monoclonal antibody (mAb) of the IgG4/kappa isotype designed to directly block the interaction between PD-1 and its ligands, PD-L1 and PD-L2. Pembrolizumab has recently been approved in the United States for the treatment of patients with unresectable or metastatic melanoma and disease progression following ipilimumab and, if BRAF V600 mutation positive, a BRAF inhibitor.

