5.5.2 Prohibited Concomitant Medications

Subjects are prohibited from receiving the following therapies during the screening and treatment phase of this trial:

- Antineoplastic systemic chemotherapy or biological therapy
- Immunotherapy not specified in this protocol
- Live vaccines within 30 days prior to the first dose of study treatment and during the treatment phase of the study. Examples of live vaccines include, but are not limited to, the following: measles, mumps, rubella, varicella/zoster, yellow fever, rabies, BCG, typhoid vaccine and intranasal influenza vaccine.
- Systemic glucocorticoids for any purpose other than to modulate symptoms from an event of clinical interest of suspected immunologic etiology. The use of physiologic doses of corticosteroids may be approved after consultation with the principal investigator.

Subjects who, in the assessment by the investigator, require the use of any of the aforementioned treatments for clinical management should be removed from the trial. At that time, subjects may receive other treatment that the investigator deems to be medically necessary.

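### Exclusion 1 names pembrolizumab where a general term for a study drug appears intended, so its 4-week washout covers no other investigational drug and its pembrolizumab part duplicates exclusion 13

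*Combined protocol and SAP*

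**What the plan says.** The list in Section 5.1.3 opens with "The subject must be excluded from participating in the trial if the subject", so each item excludes on its own. The items and sections that bear on this point are:

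- **Exclusion 1** begins "Is currently participating and receiving pembrolizumab or has participated in a study of an investigational agent and received pembrolizumab". Its first part is the current limb. Its past limb runs on to a device and a window: "has participated in a study of an investigational agent and received pembrolizumab or used an investigational device within 4 weeks of the first dose".
- **Exclusion 13** reads "Has received prior therapy with an anti-PD-1, anti-PD-L1, or anti-PD-L2 agent" and sets no time limit. Section 4.1.1 describes pembrolizumab as an antibody "designed to directly block the interaction between PD-1 and its ligands, PD-L1 and PD-L2", so it falls under this item.
- **Exclusion 5** bars earlier systemic anti-cancer treatment for bladder cancer at any time, but keeps patients with earlier intravesical treatment of any kind eligible. Section 5.1.1, Scenario 2, says the same: "Prior intravesical therapies, whether BCG, chemotherapy or otherwise, will remain eligible". Neither place gives an interval.
- **Exclusion 11** leaves any other therapy that could confound the trial to the treating physician's opinion, with no window.
- **Section 5.5** carries whatever the exclusion criteria prohibit into the on-study period.
- **Section 5.5.2** prohibits, during screening and treatment, "Antineoplastic systemic chemotherapy or biological therapy", immunotherapy from outside the protocol, live vaccines (with a 30-day limit before the first dose, BCG being one of its examples) and most systemic glucocorticoids. Investigational agents as a class are not on the list.

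**The concern.** Exclusion 1 has the structure of a recent-study washout: current participation, past participation in a study of an investigational agent, use of an investigational device, and a 4-week window. Where one expects a general term for the study drug, it names this trial's own product, twice. The effect is lopsided: a recent study device excludes a patient and a recent study drug does not. No reason is given for that difference.

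What is at stake is attribution. Safety is the primary objective (Section 3.1.1) and there is no control arm. Under Section 9.1.1, surgical complications and toxicities that prevent surgery enter the TOX count once they are judged possibly due to treatment, and a toxic death counts if it is possibly due to pembrolizumab or surgery. Under Section 5.3, a single drug-related toxicity that makes cystectomy impossible stops enrollment. A second study drug still acting, or only just stopped, makes those judgments harder, and the data have no comparator to settle them.

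**Working it through.** There is no figure in the plan to reproduce. The check is to read exclusion 1 literally and run a set of cases through every rule that could apply.

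1. **Investigational device used two weeks before the first dose.** Excluded by item 1.

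2. **Non-oncology investigational drug taken two weeks before the first dose.** Item 1 does not reach it, because the drug is not pembrolizumab. Item 5 does not, because it is not treatment for bladder cancer. Item 13 does not, unless the drug is a PD-1 or PD-L1/L2 agent. Section 5.5.2 applies only if the drug belongs to a listed class and is given during screening. Otherwise only the discretionary item 11 is left.

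3. **The same drug, still being taken at the first dose.** The current limb of item 1 names only pembrolizumab. Section 5.5 carries forward only what the exclusion criteria prohibit, so the gap carries forward too. Section 5.5.2 again depends on drug class.

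4. **Investigational intravesical agent given two weeks before the first dose.** Item 1 does not reach it. Item 5, and Section 5.1.1 for non-muscle-invasive disease, keep the patient eligible. If the agent is an immunotherapy, Section 5.5.2 bars it during screening with no limit on route. If it is another biological product, it is arguably barred too, since the word for systemic may qualify only the chemotherapy in that entry. If it is neither, only item 11 is left.

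5. **Investigational systemic anti-cancer drug for bladder cancer, at any time.** Not excluded by item 1, but excluded by item 5.

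6. **Pembrolizumab in a study more than 4 weeks before the first dose.** There are two ways to read item 1. If the window governs both the drug and the device, item 1 does not exclude this patient. If it governs the device only, item 1 does. Either way item 13 excludes the patient, so the outcome is the same.

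**Can Section 5.5.2 stand in for a 4-week washout?** The Study Flow Chart puts screening at days -28 to -1. That is at most 28 / 7 = 4 weeks, and an individual patient's screening may be shorter. Even for the classes it lists, Section 5.5.2 therefore does not guarantee 4 weeks, apart from the separate 30-day limit on live vaccines.

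Cases 2 and 3, and part of case 4, pass every explicit criterion. Case 5 is covered elsewhere. Case 6 shows duplication.

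**The case against.** Several points on the other side have force.

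- **A reader might infer that exclusions 1 and 13 contradict each other.** They do not. An exclusion criterion grants no permission, the items are cumulative, and item 13 removes every patient with earlier pembrolizumab whatever item 1 says. No patient is both allowed and barred.
- **A reader might infer that other study drugs are wholly uncontrolled.** That goes too far. Exclusion 5 and Section 5.5.2 remove systemic bladder-cancer treatment and, during screening and treatment, systemic chemotherapy, biological therapy and other immunotherapy. The 30-day limit on live vaccines mentions BCG, although whether it is meant to reach intravesical BCG is arguable.
- **Recent exposure would be seen.** Medications from the 28 days before the first dose are recorded (Sections 5.5.1 and 7.5), earlier cancer treatment is reviewed (Section 7.4), and the causality assessment in Table 5 considers other drugs as a cause. This stands, but it makes exposure visible without excluding it.
- **A reader might infer that patients who failed BCG will often have had investigational intravesical agents.** The documents do not say so. Section 4.2.1 mentions only BCG and intravesical chemotherapy. Sections 2.1.5 and 5.4 also differ on whether such patients are actively sought.
- **A reader might try to size the problem from the TOX boundary,** where one event is 1/2 of the 2-in-5 limit, 1/3 of the 3-in-9 limit and 1/20 = 5 percentage points of the final rate. Those fractions hold for any single misattributed event and do not measure this gap. TOX is also narrow, and nothing in the documents shows that such drugs commonly cause TOX events.

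These arguments narrow the point. None of them supplies the missing washout for the remaining drugs.

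**Conclusion.** The point holds in a limited form. As written, the washout in exclusion 1 reaches investigational devices but no investigational drug except pembrolizumab, and for pembrolizumab it is redundant with exclusion 13. The remaining gap is mainly recent or concurrent non-oncology study drugs, and intravesical study drugs that are neither immunotherapy nor biological. For these the only control is individual opinion under exclusion 11.

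The consequence is possible blurring of attribution in a 20-patient single-arm safety study. It cannot be sized, because the documents give no number of patients with such exposure.

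The conclusion rests on a literal reading of exclusion 1. That a general term was intended is an inference from how the sentence is built, since the documents do not state it. The gap in the text does not depend on that inference. This is an operative eligibility rule, so it merits correction even though few patients may be affected.

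**What to change.** Reword exclusion 1 along these lines: *Is currently in a study and receiving an investigational agent; or, in the 4 weeks before the first dose of study treatment, has received an investigational agent or used an investigational device.* The interval is the protocol's own. Leave prior pembrolizumab to exclusion 13. Because Section 5.5 carries the exclusion criteria into the on-study period, the new wording would also address concurrent study drugs.

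The sponsor should then reconcile exclusion 1 with the statements in Section 5.1.1 and exclusion 5 that prior intravesical therapies remain eligible, and say whether these extend to recent investigational intravesical agents. The eligibility of intravesical treatment is stated twice and looks deliberate. Narrowing it would be a new restriction and is the sponsor's decision, beyond correcting a slip.

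The cost is a wording amendment and an occasional patient who is delayed or not enrolled.

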5.2 Study Treatment

The treatment to be used in this trial is outlined below in Table 2

Table 2: Trial Treatment:

Drug	Dose/ Potency	Dose Frequency	Route of Administration	Regimen/ Treatment Period	Use
Pembrolizumab	200 mg	Q3W x 2	IV infusion	Day 1 of each 3 week cycle	Experimental

5.2.1 Dose Selection

The rationale for selection of doses to be used in this trial is provided in Section 4.2.2.

Details on preparation and administration of pembrolizumab are provided in the Pharmacy Manual.

5.2.2 Dose Modification and toxicity management for immune-related AEs associated with pembrolizumab

AEs associated with pembrolizumab exposure may represent an immunologic etiology. These immune-related AEs (irAEs) may occur shortly after the first dose or several months after the last dose of pembrolizumab treatment and may affect more than one body system simultaneously. Therefore, early recognition and initiation of treatment is critical to reduce complications. Based on existing clinical study data, most irAEs were reversible and could be managed with interruptions of pembrolizumab, administration of corticosteroids and/or other supportive care. For suspected irAEs, ensure adequate evaluation to confirm etiology or exclude other causes. Additional procedures or tests such as bronchoscopy, endoscopy, skin biopsy may be included as part of the evaluation. Based on the severity of irAEs, withhold or permanently discontinue pembrolizumab and administer corticosteroids. Dose modification and toxicity management guidelines for irAEs associated with pembrolizumab are provided in Table 3.

Table 3: Dose modification and toxicity management guidelines for immune-related AEs associated with pembrolizumab

General instructions:

1. Corticosteroid taper should be initiated upon AE improving to Grade 1 or less and continue to taper over at least 4 weeks.
2. For situations where pembrolizumab has been withheld, pembrolizumab can be resumed after AE has been reduced to Grade 1 or 0 and corticosteroid has been tapered. Pembrolizumab should be permanently discontinued if AE does not resolve within 12 weeks of last dose or corticosteroids cannot be reduced to ≤ 10 mg prednisone or equivalent per day within 12 weeks.
3. For severe and life-threatening irAEs, IV corticosteroid should be initiated first followed by oral steroid. Other immunosuppressive treatment should be initiated if irAEs cannot be controlled by corticosteroids.

Immune-related AEs	Toxicity grade or conditions (CTCAEv4.0)	Action taken to pembrolizumab	irAE management with corticosteroid and/or other therapies	Monitor and follow-up

Proprietary Information of MD Anderson

2017-0057

January 9, 2019

Page 17

Pneumonitis	Grade 2	Withhold	
 Administer corticosteroids (initial dose of 1-2 mg/kg prednisone or equivalent) followed by taper 	
 Monitor participants for signs and symptoms of pneumonitis Evaluate participants with suspected pneumonitis with radiographic imaging and initiate corticosteroid treatment Add prophylactic antibiotics for opportunistic infections
	Grade 3 or 4, or recurrent Grade 2	Permanently discontinue		
Diarrhea / Colitis	Grade 2 or 3	Withhold	
 Administer corticosteroids (initial dose of 1-2 mg/kg prednisone or equivalent) followed by taper 	
 Monitor participants for signs and symptoms of enterocolitis (ie, diarrhea, abdominal pain, blood or mucus in stool with or without fever) and of bowel perforation (ie, peritoneal signs and ileus). Participants with \geq Grade 2 diarrhea suspecting colitis should consider GI consultation and performing endoscopy to rule out colitis. Participants with diarrhea/colitis should be advised to drink liberal quantities of clear fluids. If sufficient oral fluid intake is not feasible, fluid and electrolytes should be substituted via IV infusion.
	Grade 4	Permanently discontinue		
AST / ALT elevation or Increased bilirubin	Grade 2	Withhold	
 Administer corticosteroids (initial dose of 0.5- 1 mg/kg prednisone or equivalent) followed by taper 	
 Monitor with liver function tests (consider weekly or more frequently until liver enzyme value returned to baseline or is stable)
	Grade 3 or 4	Permanently discontinue		
Type 1 diabetes mellitus (T1DM) or Hyperglycemia	Newly onset T1DM or Grade 3 or 4 hyperglycemia associated with evidence of β -cell failure	Withhold	
 Initiate insulin replacement therapy for participants with T1DM Administer anti-hyperglycemic in participants with hyperglycemia 	
 Monitor participants for hyperglycemia or other signs and symptoms of diabetes.
Hypophysitis	Grade 2	Withhold	
 Administer corticosteroids and initiate hormonal replacements as clinically indicated. 	
 Monitor for signs and symptoms of hypophysitis (including hypopituitarism and adrenal insufficiency)
	Grade 3 or 4	Withhold or permanently discontinue ¹		
Hyperthyroidism	Grade 2	Continue		
 Monitor for signs and symptoms of thyroid disorders.

	Grade 3 or 4	Withhold or permanently discontinue ¹	
 Treat with non-selective beta-blockers (eg, propranolol) or thionamides as appropriate 	
Hypothyroidism	Grade 2-4	Continue	
 Initiate thyroid replacement hormones (eg, levothyroxine or liothyroinine) per standard of care 	
 Monitor for signs and symptoms of thyroid disorders.
Nephritis and Renal dysfunction	Grade 2	Withhold	
 Administer corticosteroids (prednisone 1-2 mg/kg or equivalent) followed by taper. 	
 Monitor changes of renal function
	Grade 3 or 4	Permanently discontinue		
Myocarditis	Grade 1 or 2	Withhold	
 Based on severity of AE administer corticosteroids 	
 Ensure adequate evaluation to confirm etiology and/or exclude other causes
	Grade 3 or 4	Permanently discontinue		
All other immune-related AEs	Intolerable/ persistent Grade 2	Withhold	
 Based on type and severity of AE administer corticosteroids 	
 Ensure adequate evaluation to confirm etiology and/or exclude other causes
	Grade 3	Withhold or discontinue based on the type of event. Events that require discontinuation include and not limited to: Gullain-Barre Syndrome, encephalitis		
	Grade 4 or recurrent Grade 3	Permanently discontinue		

1. Withhold or permanently discontinue pembrolizumab is at the discretion of the investigator or treating physician.

NOTE:

For participants with Grade 3 or 4 immune-related endocrinopathy where withhold of pembrolizumab is required, pembrolizumab may be resumed when AE resolves to ≤ Grade 2 and is controlled with hormonal replacement therapy or achieved metabolic control (in case of T1DM).

Dose modification and toxicity management of infusion-reactions related to pembrolizumab

Pembrolizumab may cause severe or life threatening infusion-reactions including severe hypersensitivity or anaphylaxis. Signs and symptoms usually develop during or shortly after drug infusion and generally resolve completely within 24 hours of completion of infusion. Dose modification and toxicity management guidelines on pembrolizumab associated infusion reaction are provided in Table 4.

Table 4 Pembrolizumab Infusion Reaction Dose modification and Treatment Guidelines

Proprietary Information of MD Anderson

2017-0057

January 9, 2019

Page 20

NCI CTCAE Grade	Treatment	Premedication at Subsequent Dosing
Grade 1 Mild reaction; infusion interruption not indicated; intervention not indicated	Increase monitoring of vital signs as medically indicated until the participant is deemed medically stable in the opinion of the investigator.	None
Grade 2 Requires therapy or infusion interruption but responds promptly to symptomatic treatment (e.g., antihistamines, NSAIDs, narcotics, IV fluids); prophylactic medications indicated for ≤24 hrs	
Stop Infusion.
 
Additional appropriate medical therapy may include but is not limited to:
 
IV fluids Antihistamines NSAIDs Acetaminophen Narcotics
 
Increase monitoring of vital signs as medically indicated until the participant is deemed medically stable in the opinion of the investigator.
 
If symptoms resolve within 1 hour of stopping drug infusion, the infusion may be restarted at 50% of the original infusion rate (e.g. from 100 mL/hr to 50 mL/hr). Otherwise dosing will be held until symptoms resolve and the participant should be premedicated for the next scheduled dose.
 
Participants who develop Grade 2 toxicity despite adequate premedication should be permanently discontinued from further study drug treatment
	
Participant may be premedicated 1.5h (± 30 minutes) prior to infusion of _____ with:
 
Diphenhydramine 50 mg po (or equivalent dose of antihistamine).
 
Acetaminophen 500-1000 mg po (or equivalent dose of analgesic).

Grades 3 or 4 Grade 3: Prolonged (i.e., not rapidly responsive to symptomatic medication and/or brief interruption of infusion); recurrence of symptoms following initial improvement; hospitalization indicated for other clinical sequelae (e.g., renal impairment, pulmonary infiltrates) Grade 4: Life-threatening; pressor or ventilatory support indicated	
Stop Infusion.
 
Additional appropriate medical therapy may include but is not limited to:
 
Epinephrine** IV fluids Antihistamines NSAIDs Acetaminophen Narcotics Oxygen Pressors Corticosteroids
 
Increase monitoring of vital signs as medically indicated until the participant is deemed medically stable in the opinion of the investigator.
 
Hospitalization may be indicated.
 
**In cases of anaphylaxis, epinephrine should be used immediately.
 
Participant is permanently discontinued from further study drug treatment.
	No subsequent dosing

Appropriate resuscitation equipment should be available at the bedside and a physician readily available during the period of drug administration.
 
For further information, please refer to the Common Terminology Criteria for Adverse Events v4.0 (CTCAE) at http://ctep.cancer.gov
		

